### **Sample Population:**

Inclusion/exclusion criteria – the study population will be derived from the two participating BSW hospital systems (Waco and Temple, TX) and will be selected to participate in the study on the basis of the following criteria (inclusion): Age  $>18$  and  $\leq 79$  years, written informed consent, ability to perform informed consent, FOLFOX treatment and Stage II/III colon cancer diagnosis. To ensure fitness for recurrence detection and anti-cancer therapy, the age was restricted to  $>18$  so as not to include minors, and  $\leq 79$  years based on life expectancy with colon cancer diagnosis. Individuals will be excluded from participating if any of the following criteria are met: not diagnosed with stage II or III colon cancer, pregnancy, Lynch syndrome or FAP diagnosis, inability or refusal to perform informed consent, inability to comply with the follow-up program, history of previous colon cancer diagnosis, previous treatment with antibiotics in the last month, previous bowel resection.

Sample size - Based on current data from BSW, the recurrence rate for stage II/III colon cancer is 20%, with a 10% 5-year survival rate for stage IV colon cancer. Given our study design, we conducted power calculations for each group. To meet the number required to detect chemotherapy induced diarrhea and mucositis associated with microbial and metabolite abundance, we need to collect at least 560 stool samples from 112 people (Observational Study). To meet the power requirements for detection of differentially abundant microbes and metabolites associated with chemotherapy-induced CID we estimate needing at least 100 stage II/III patients. The specific power calculation for these groups are provided below.

### Taxonomic differential abundance analysis

Power calculations for differential abundance analysis in human microbiome studies can be challenging, as there is limited data with highly consistent sample preparation available and uncertainty in the overall distribution of bacterial taxa throughout the human population. Recently, a CRC stool-based microbiome study of a large cohort was performed by Baxter and colleagues. This publicly available data serves as a potential resource for power-analyses by allowing for empirical calculation of the expected variability of taxa in both healthy and CRC-associated gut microbiomes.

We obtained the raw 16S rRNA sequence data from the Baxter study including patients with CRC (n=120) and healthy controls (n=172). After preprocessing and subsampling high-quality reads to an equivalent depth of 10,000 per sample, we identified 92 genus-level groups that each represented (on average) at least 0.25% of sequences from the CRC or healthy patient groups. We then computed the corresponding variance in relative abundance for each of these 92 taxa, and used the empirical values to perform a comprehensive power-analysis.

As expected, increased statistical power was found with higher abundance genera, so here we focus on power results for organisms reflecting an average of 0.25-1.0% of 16S sequences in the gut microbiome because detecting differences in these rare taxa may be critical to our study. Among the genera found at this low level, if we assume equal variance in two normally-distributed populations and require a significance level of  $\alpha=0.05$ , we expect that with a comparison of 40 vs 100 individuals, we will be able to detect a relative increase of 200% (e.g. 0.5% mean abundance increased to 1.5%), with a statistical power of 92.3% (*pwr.t2n.test* in R).

Considering the genera with average frequency  $>1\%$ , we estimate that with a 40 vs 100 sample comparison, we will be able to detect a relative increase of 200% (e.g. 1% mean abundance increased to 3%, or 2% mean abundance increased to 6%), with an expected statistical power of 99.6%.

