**Table summarizing results for power in detecting differential abundance:**

		Taxa Abundance	Group Sizes			
			20vs100	40vs100	50vs100	75vs100
Relative difference	50%	0.25-1.0%	20.5%	30.6%	34.2%	40.6%
		>1.0%	40.0%	54.9%	59.3%	66.4%
	100%	0.25-1.0%	52.7%	67.2%	71.0%	76.5%
		>1.0%	77.7%	88.8%	91.2%	94.5%
	200%	0.25-1.0%	84.6%	92.3%	93.9%	96.0%
		>1.0%	97.9%	99.6%	99.8%	99.9%
	300%	0.25-1.0%	95.0%	98.2%	98.7%	99.3%
		>1.0%	99.9%	100.0%	100.0%	100.0%

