and microbial clusters (community state types) at baseline using Kruskall-Wallis, and for individual taxa using Pairwise Spearman correlations. We will use PERMANOVA for comparing beta-diversity (weighted UniFrac distances) at baseline by levels of macro- and micronutrients. DESeq2, Kruskall-Wallis and Mann-Whitney tests will be conducted to identify significant differences in tissue and stool taxa or microbial clusters according HEI scores at baseline. The Benjamini and Hochberg false discovery rate (FDR) will be used to correct for multiple testing. Taxa or microbial clusters found to be significantly differentially abundant between treatment time points and baseline will be used to conduct 'random forest' modeling, as previously described, to identify dietary factors that best predict changes in these taxa or clusters. Additionally, we will investigate the tissue and stool microbiome-diet relationship using principal components analysis to identify significant trends among the dietary factors using coinertia analysis. To investigate the microbiome-diet relations during treatment, we will use the microbial clusters and calculate the  $\log_2$  fold change in the clusters from baseline. We will then determine how much the clusters change from baseline according to dichotomous values of macronutrients.

**Microbiome-treatment analysis:** To evaluate differential abundance comparing treatment time points to baseline (prior to surgery and post-surgery/pre-treatment), DESeq2 will be used to control operational taxonomic unit (OTU) over-dispersion between replicates; OTUs will be considered significantly differentially abundant between time points if the false discovery rate (FDR) corrected p-value is below 0.1. A change in relative abundance will be defined as a fold change between mean log relative abundance during treatment phase (week 4, 14, 24) and baseline (prior to surgery). Taxa found to be significantly differentially abundant between treatment time points and baseline (FDR corrected p-value  $<0.05$ ) will be put into an adjusted regression model to control for age, education, income level, marital status, and activity level, diet quality (HEI), tumor stage, medical history with p-values corrected for multiple hypothesis testing using FDR adjustment.

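### The 92.3% power and its table fix each genus's SD while its mean rises by up to 300%; the table's own implied CVs make that untenable, and no planned analysis is the test that was powered.

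*Protocol*

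**What the plan says.** The sample-size paragraph (Protocol, Sample Population) asks for at least 100 stage II/III patients to detect microbes and metabolites associated with chemotherapy-induced diarrhea (CID), and refers to the calculation that follows it.

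That calculation (Taxonomic differential abundance analysis) takes one empirical variance per genus from a public 16S dataset, for 92 genera at a depth of 10,000 reads. It then computes power "if we assume equal variance in two normally-distributed populations" at alpha 0.05. For genera at 0.25-1.0% abundance, "with a comparison of 40 vs 100 individuals", it concludes: "we will be able to detect a relative increase of 200% (e.g. 0.5% mean abundance increased to 1.5%), with a statistical power of 92.3" percent, naming the R function pwr.t2n.test. For genera above 1% the corresponding figure is 99.6%. The table that follows is indexed by "Relative difference" (50%, 100%, 200%, 300%) and four pairs of group sizes. No SD, CV or dispersion is printed.

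The analyses named elsewhere are different:
- **Bioinformatics overview:** Mann-Whitney tests with FDR correction between time points.
- **Section 4.4, CID and mucositis:** random forest, then logistic regression and ROC curves.
- **Section 4.4, treatment time points against baseline:** "DESeq2 will be used to control operational taxonomic unit (OTU) over-dispersion between replicates". DESeq2 is also named, beside rank tests, for diet score at baseline.

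**The concern.** The effect is defined as a ratio, but the noise is held at its un-increased value. When a skewed, non-negative quantity is multiplied by three, its SD is also multiplied by three. A calculation that triples the mean and keeps the SD credits the whole increase as signal.

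This matters because these are the only power figures behind the 100 to 112 patients, and because the section says that detecting differences in rare taxa may be critical to the study. If the figures are optimistic, a null result for a low-abundance genus would be read as stronger evidence of no change than it is.

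**Working it through.** **Inputs.** Group sizes 40 vs 100, alpha 0.05, relative increase r = 2 (mean tripled) and depth 10,000 come from the Protocol. Two-sided testing is the default of the named function. The CVs are not printed and are back-solved below. Mean counts are assumed to be 50 reads (0.5% of 10,000) for the low band and 200 reads for genera above 1%.

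**Step 1: reproduce the printed table.** With constant SD, d = r/CV. Power is two-sided noncentral t with n1 + n2 − 2 degrees of freedom and noncentrality d × √(n1n2/(n1+n2)), averaged over genera.
- A single CV cannot reproduce the low-abundance cells; the CV implied by each cell runs from 1.79 to 4.42.
- A mixture of CVs matches all 16 low-abundance cells, and separately all 16 cells above 1%, within about 0.03 points. The headline cell gives 92.3%.
- About 99% of the low-band weight lies at CVs of about 1.2 to 5.3.
- A simpler two-parameter lognormal distribution of CVs (median about 2.1, SD of log about 0.51) is within about 1.2 points everywhere and gives 92.9%.

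The table is thus an average of constant-SD t-test powers. This does not independently check the source variances.

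**Step 2: is the premise tenable?** A normal variable with mean m and SD = CV × m falls below zero with probability Φ(−1/CV). At CV 1.2 this is Φ(−0.83) = 20%; at CV 5.3 it is Φ(−0.19) = 43%. Abundance cannot be negative, so normality fails across the range that the table itself implies.

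**Step 3: let the variance follow the mean.** For a negative binomial Wald test on the log fold change:
- dispersion = CV² − 1/50
- SE² = (1/150 + dispersion)/40 + (1/50 + dispersion)/100
- power ≈ Φ(ln 3/SE − 1.96)

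For one genus at CV 2.13, the constant-SD calculation has d = 2/2.13 = 0.94 and power 99.9%. Under the negative binomial, dispersion = 4.517, SE = 0.398, ln 3/SE = 1.099/0.398 = 2.76, and power = Φ(0.80) = 79%.

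Averaged over the back-solved CVs, 40 vs 100:

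| Genera | Increase | Printed | Negative binomial Wald |
|---|---|---|---|
| 0.25-1.0% | +100% | 67.2% | about 48% |
| 0.25-1.0% | +200% | 92.3% | about 72% |
| >1% | +100% | 88.8% | about 73% |
| >1% | +200% | 99.6% | about 92% |

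Four alternative fits of the CV distribution give 71.0-72.0% for the headline cell.

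**Step 4: other tests for the 92.3% cell, same CVs.**
- Welch t on raw abundance, SD proportional to the mean, normal-theory formula: about 52% if the group of 40 has the higher mean, about 72% if the group of 100 does.
- Pooled or Welch t, simulated counts: about 53-75% with gamma-type counts and 70-87% with lognormal counts.
- Mann-Whitney, simulated: about 50% with gamma-type counts, about 97% with lognormal.
- t-test on the log scale, lognormal data: about 98%.

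**The case against.** Several points on the other side are sound.

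1. **The assumption is stated openly and the arithmetic is right for it.** This stands. The fault lies in the premise and in presenting the result as what the study will be able to detect.

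2. **DESeq2 is not the test for the contrast that is said to be powered.** This also stands. The sample-size paragraph speaks of CID, for which Section 4.4 plans random forest and logistic regression. DESeq2 is named for time points and diet score, and the time-point analysis uses an FDR threshold, not an unadjusted 0.05. A reader might infer that the planned test has 72% power. The Protocol does not support that, because no independent 40 vs 100 DESeq2 comparison is assigned to CID.

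3. **The 72% depends on quantities that are not printed.** True. It needs back-solved CVs, assumed mean counts, a CV unchanged by the effect, and a Wald formula with known dispersion.

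4. **A loss of power is not certain.** A reader might infer that every realistic model lowers the figure. Lognormal data with a rank or log-scale test give about 97-98%, above the printed value. High CVs may also reflect many zeros. If the mean rises because more patients carry the genus, variance rises about threefold rather than ninefold, and the Welch formula then gives roughly 78-87%.

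Points 3 and 4 limit what can be said about size and direction. They do not rescue the 92.3%: the answer ranges from about 50% to 98% according to a distribution that the calculation left out.

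**Conclusion.** The point holds in a limited form. The power figures rest on a constant-SD normal model that the table's own implied CVs contradict, and they describe a test that is not among the planned analyses. The 92.3% and 99.6% should not stand as the power of those analyses.

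For the headline cell, the plausible values are about 72% (negative binomial), about 52-72% (Welch t by formula, SD proportional to the mean) and about 50-97% (rank test, depending on shape). All rest on CVs back-solved from the printed table, so they show how sensitive the figure is; none replaces it. The size and direction of the error for the CID analysis cannot be settled from the Protocol alone. The sponsor can settle them, since the per-genus variances were computed.

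**What to change.** Using the public dataset already obtained, recompute the table by multiplying one group's abundances by (1 + relative difference), so that the SD scales with the mean. Apply the test actually planned for the contrast being powered, and name that contrast and test beside the table. Report the per-genus CV or dispersion, or its distribution within each abundance band. Replace the 92.3%, the 99.6% and the table entries with the result, or with a range if it depends materially on the assumed distribution.

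If this is not done, state that the figures hold only for a constant-SD shift tested by an equal-variance t-test and are not the power of the planned analyses.

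The cost is a few hours of re-analysis and a wording change in the power section. Enrolment does not change. The downside is that the printed power may be less favourable.

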#### **4.4 Data Analysis.**

Classification of taxa associated with side effects or severity: Recently, in an animal model of colon tumorigenesis (AOM/DSS), investigators used the initial microbial community structure (16s rRNA sequencing) to predict tumor burden after exposure to various antibiotics during colon carcinogenesis. In order to conduct a similar analysis and reduce data dimensionality, we will first perform cluster modeling using Dirichlet multinomial mixtures (Holmes et al. 2012) to identify microbial clusters (community state types). To determine which taxa or taxonomic cluster are the best predictors of treatment side effects (CID, mucositis) and severity (stage 3-4), we will conduct 10-fold cross-validation using the RandomForest package (Version 3.6.4) in R (R-studio, Version 0.98.1091; Boston, MA). Specifically, 5,000 trees will be used and the parameter mtry will be set at 100. The taxa with the highest importance scores will be used for further analysis. This procedure will be tested by splitting the data into test and training sets, then running Random Forest using the same procedure described above on the training dataset and comparing the predictive accuracy of the top taxa (based on importance scores) in the test set. Based on this 10-fold cross-validation, we will be able to calculate sensitivity and specificity. These top taxa will then be used to generate receiver operator curves (ROC) and calculate area under the curve (AUC). Each microbial cluster or taxa will undergo independent logistic regression testing to calculate area under the ROC curve using Stata (v13). The command roccomp will be used to compare statistical difference between AUCs and determine the best combination of taxa for classification of CID or mucositis and for severity.

Microbiome-Diet Analysis: To evaluate the impact of diet on the stool and tissue microbiome, we will use the dietary analysis generated from the ASA24 and DHQIII, which includes the Healthy Eating Index (HEI). Prior to analysis, we will conduct normality testing for each variable using Shapiro-Wilk test. For any variables that do not pass, a logarithm transformation will be performed. In order to identify any potentially important diet or nutrient-microbiome associations, we will conduct correlation analysis between dietary macronutrients (carbohydrates, fats, proteins) or micronutrients (vitamins and minerals)

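### The published power figures are for unnamed groups of 120 to 175 people at an unadjusted 0.05, not for the CID versus no-CID comparison within 112 patients that the sample size is meant to support

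*Protocol*

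**What the plan says.** The sample-size paragraph (Protocol, Sample Population) gives CID as the purpose. For "detection of differentially abundant microbes and metabolites associated with chemotherapy-induced CID we estimate needing at least 100 stage II/III patients". For CID and mucositis together, it says "we need to collect at least 560 stool samples from 112 people (Observational Study"). It then points to the supporting calculation: "The specific power calculation for these groups are provided below".

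The next section, Taxonomic differential abundance analysis, takes per-genus variances from a published stool dataset of 120 colorectal cancer patients and 172 healthy controls. Its model is "if we assume equal variance in two normally-distributed populations and require a significance level of" 0.05, and its headline result is "we expect that with a comparison of 40 vs 100 individuals, we will be able to detect a relative increase of 200"%, with power of 92.3% for genera at 0.25-1.0% abundance and 99.6% for genera above 1%. It focuses on the low-abundance genera because "detecting differences in these rare taxa may be critical to our study". The power table has columns for 20, 40, 50 and 75 versus 100. Neither group is named and no CID rate is used.

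In section 4.4, the taxa-CID analysis looks for the "best predictors of treatment side effects (CID, mucositis) and severity (stage 3-4"), then: "Each microbial cluster or taxa will undergo independent logistic regression testing to calculate area under the ROC curve using Stata (v13"). It states no significance or FDR level. The Metabolite-CID paragraph plans logistic regression on CID present or absent, at baseline and at single time points, with FDR below 0.05. It describes this as similar to the microbiome-CID analysis.

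**The concern.** The document presents the table as the justification for 112 patients in a CID analysis, but the table describes a different comparison. CID versus no-CID divides the treated cohort into two parts, so the two group sizes must add up to at most 112. No column does.

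The non-cancer volunteers whose stool may be kept as control material (section 4.3, Subject recruitment and enrollment) cannot fill the gap. They do not receive FOLFOX, so they belong to neither CID group, and their number is not stated. The own-control design in section 4.3 (Study procedures) does not explain the table either, because that comparison would be paired rather than between two independent populations.

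A reader who takes 92.3% as the chance of detecting a threefold difference in a rare genus between patients with and without CID is relying on a figure that was not calculated for that question. The figure is also per-test, although many genera (92 met the abundance threshold) are to be examined.

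**Working it through.** **1. Group totals (Protocol table).** 20+100 = 120; 40+100 = 140; 50+100 = 150; 75+100 = 175. All exceed 112.

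**2. Information in each comparison.** With equal variances, as the Protocol assumes, the power of a two-sample t-test depends on group size essentially through n1·n2/(n1+n2).

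| Comparison | n1·n2/(n1+n2) | Even-group total with the same information (4 × that) |
|---|---|---|
| 20 vs 100 | 16.7 | 66.7 |
| 40 vs 100 | 28.6 | 114.3 |
| 50 vs 100 | 33.3 | 133.3 |
| 75 vs 100 | 42.9 | 171.4 |
| 56 vs 56 (maximum for 112) | 28.0 | 112 |
| 50 vs 50 (maximum for 100) | 25.0 | 100 |
| 67 vs 45 | 26.9 | 107.7 |
| 22 vs 90 | 17.7 | 70.7 |

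Three of the four columns exceed what any split of 112 can supply; the 40 vs 100 column does so only narrowly. Setting n1(112 − n1)/112 = 16.7 gives n1 = 20.4. If the smaller CID group has about 20 patients or fewer, power falls below even the 20 vs 100 column.

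**3. The Protocol's own figure.** The per-genus standard deviations are not given, so 92.3% cannot be computed from stated inputs. Solving the noncentral-t power equation for 92.3% at 40 vs 100, two-sided 0.05, gives a standardized difference of 0.638. That single value predicts 73.3%, 92.3%, 95.5% and 98.6% across the four columns, but the table shows 84.6%, 92.3%, 93.9% and 96.0%. The table therefore looks like an average of power over genera with different variability.

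A lognormal spread of the mean/SD ratio across genera (an assumption) fits the whole table well:
- 0.25-1.0% genera: median 0.469, log-SD 0.511, root-mean-square error 0.57 points over 16 cells.
- Genera above 1%: median 0.759, log-SD 0.449, root-mean-square error 0.20 points.

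The table is thus internally consistent with a two-sided, unadjusted 0.05.

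**4. Fitted model applied to splits of the cohort**, 0.25-1.0% genera, unadjusted 0.05:

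| Split | 200% increase | 100% increase |
|---|---|---|
| 40 vs 100 (Protocol states 92.3%, 67.2%) | 92.9% | 66.3% |
| 56 vs 56 | 92.6% | 65.7% |
| 67 vs 45 | 92.2% | 64.7% |
| 50 vs 50 | 91.3% | 62.6% |
| 22 vs 90 | 86.3% | 53.4% |

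**5. Adding multiplicity.** With 92 genera at an unadjusted 0.05, 92 × 0.05 = 4.6 false positives are expected if none truly differs. For Benjamini-Hochberg at q = 0.05, the average per-test threshold a solves a = q·[π·Power(a) + (1 − π)·a], where π is the share of taxa that truly differ. The Protocol gives no π, so a range is shown and tests are taken as independent.

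| Class, increase, split | π = 1% | 5% | 10% | 20% | 50% |
|---|---|---|---|---|---|
| 0.25-1.0%, 200%, 56/56 | 71.7 | 79.3 | 82.6 | 85.8 | 89.7 |
| 0.25-1.0%, 200%, 50/50 | 67.8 | 76.2 | 79.8 | 83.4 | 87.8 |
| 0.25-1.0%, 200%, 22/90 | 55.8 | 65.7 | 70.2 | 74.8 | 80.9 |
| 0.25-1.0%, 100%, 56/56 | 22.4 | 31.8 | 37.1 | 43.1 | 52.5 |
| Above 1%, 200%, 56/56 | 94.5 | 96.7 | 97.5 | 98.2 | 98.9 |

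Entries are average power in per cent.

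**The case against.** **The headline figure nearly survives.** The text relies only on 40 vs 100. The one CID rate in the document, over 50% (section 2, Significance), suggests a fairly even split, at which the fitted power is 92.6% (56/56) or 92.2% (67/45). The difference from the fitted 92.9% at 40 vs 100 is about the size of the fitting error. This stands: group size alone does little harm if CID is near half.

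**The larger losses rest on assumptions.** The taxa-CID paragraph states no FDR level, so multiplicity is inferred from the metabolite paragraph. The share of taxa that truly differ and the 22/90 split are not in the document, and the sizing sentence does not claim power for severe CID. This also stands, and it is why ranges are shown. But the background CID rate never enters the power calculation, and section 4.4 does plan to predict severity.

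**Repeated stools add information.** If three on-treatment samples per patient were combined, information would rise by 3/(1+2ρ), where ρ is the within-person correlation. At an assumed ρ of 0.9, 28.0 becomes 30.0; at 0.5 it becomes 42.0. This does not rescue the table. The CID tests set out in section 4.4 are logistic regressions per taxon or cluster, and per metabolite at baseline and at individual time points. The mixed models there address change from baseline.

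**The settings are visible and the study is formative.** The level, group sizes and R function stand beside 92.3%, and per-taxon power is commonly reported. A careful reader can see the figure is unadjusted, but cannot see that the groups are not the CID groups the preceding paragraph promises.

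**Conclusion.** The point holds. From the document alone, the power table is not the calculation that the sample-size paragraph says it is. Every column needs more people than the cohort has, and three of the four carry more information than any CID split of 112 can provide. The 92.3% and 99.6% are per-test figures for a comparison the design does not contain.

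The practical size depends on facts the Protocol does not give. At an even split and per test, the loss is under one point. At an assumed 22/90 split, 92.3% becomes about 86%. Under an inferred 5% FDR with 1-50% of taxa truly different, it becomes about 72-90% at 56/56 and about 56-81% at 22/90. The 99.6% for genera above 1% becomes about 95-99% at 56/56. These figures rest on the back-fitted lognormal effect distribution and, for FDR, on independent tests. They illustrate the loss and do not replace the Protocol's calculation. The error should be corrected, but it does not call the target of 112 into question.

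**What to change.** Keep 112 patients and make these edits to the sample-size paragraph, the power section and the table:

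- Name CID versus no-CID as the comparison being powered.
- Replace the four columns with splits that add up to the expected evaluable number. State the CID rate used and, if severity is to be powered, the expected grade 3-4 rate.
- Either compute power at a stated FDR level with the assumed share of taxa truly different, or label the figures per-test and unadjusted.
- Say that the t-test approximates the per-taxon logistic regression in section 4.4.
- Restate 92.3% and 99.6% on that basis.

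The cost is a rerun of the existing power script, two edited paragraphs and one edited table. Recruitment, design and analysis do not change. The stated power for rare genera will probably look less favourable.
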